### 5.9.2 DM199 Laboratory

Pre-dose sample collection for plasma concentration of DM199 and pharmacodynamic biomarkers will be collected, stored, and shipped according to the Central Laboratory Manual at baseline and on days 2, 22, and 90. Urinary KLK1 concentration will be collected, stored, and shipped according to the Central Laboratory Manual at baseline and days 4, 13, 22 and 90.

**Table 3** describes the parameters to be measured.

**Table 3: DM199 Laboratory Collection Parameters**

Analysis	Parameters
Pharmacokinetic biomarkers	Plasma concentration of DM199
Diagnostic biomarkers	Urinary concentration of KLK1
Pharmacodynamic biomarkers	CRP, MMP-9, VEGF, Nitric Oxide [NOx], Prostaglandins [E2], DM199 ADA, and tPA

## 5.10 INTRAVENOUS TREATMENT ADMINISTRATION

After it is confirmed that all eligibility criteria have been met, study treatment has been assigned through the randomization system, and all pre-dosing (baseline) assessments are complete, a single 40-minute IV infusion of DM199 or placebo will be administered on day 1. Refer to **4. Study Treatment** and the pharmacy manual for information on proper storage, dosing, and administration.

### 5.11 SUBCUTANEOUS TREATMENT ADMINISTRATION

A single subcutaneous dose of DM199 or placebo will be administered between 2 and 12 hours after the start time of the IV dose. Additional doses will then occur every 72 ( $\pm$  2) hours after the first SC dose for the duration of the 22-day treatment period. In total, eight SC doses must be administered. Refer to **4. Study Treatment** and the pharmacy manual for information on proper storage, dosing, and administration.

Note: The treatment period (days 1-22) are defined by the time of the IV dose of study treatment rather than calendar days. Therefore, the first SC dose administered between 2 and 12 hours post IV may occur within the same calendar day or the day after. Caution should be taken to adjust all subsequent SC doses based on the required 72 ( $\pm$  2) window and required testing that is to occur on dosing days, including: body weight, height, and BMI calculation; vital sign measurements; urine sample for KLK1 concentration, and clinical labs.

### 5.12 NIH STROKE SCALE

For subjects undergoing reperfusion treatment prior to study enrollment the NIH stroke scales (NIHSS) must occur at least one hour after treatment. The scale will also be administered at days 22 and 90.

A NIHSS of  $\geq 6$  and  $\leq 25$  at enrollment is required for study inclusion.

The NIHSS will be administered by the Investigator or a designated and trained member of the study team.

### 5.13 BARTHEL INDEX

The Barthel Index will be administered at baseline (any time prior to first dose of study treatment), days 22 and 90 by the Investigator or a designated and trained member of the study team.

### 5.14 MODIFIED RANKIN SCALE

The Modified Rankin Scale (MRS) be administered at baseline (any time prior to first dose of study treatment), days 22 and 90 by the Investigator or a designated and trained member of the study team.

### 5.15 SUBJECT WITHDRAWAL

Participation in the study is strictly voluntary. A subject has the right to withdraw from the study at any time for any reason.

The Investigator has the right to terminate the participation of a subject for any of the following reasons:

- The need to take medication which may interfere with study assessments

- Subject's non-compliance with study requirements
- Difficulties in obtaining blood samples
- Severe or serious adverse events (SAEs), or for any other reason relating to the subject's safety or integrity of the study data

If a subject is withdrawn from the study, the Medical Monitor will be informed immediately. If there is a medical reason for withdrawal, the subject will remain under the supervision of the Investigator until satisfactory health has returned.

The reasons for withdrawal will be recorded on the eCRF and included in the final clinical study report, along with any AEs and any necessary medical treatment. In the event that a subject is discontinued from the study due to a significant AE, SAE, or abnormal laboratory result (refer to **6.2.4 Clinical Laboratory Abnormalities and Other Abnormal Assessments**), the Investigator or medically trained designee will evaluate the urgency of the event. If the situation warrants, the Investigator or medically trained designee will take appropriate diagnostic and therapeutic measures. If the situation is not an immediate emergency, the Investigator, or medically trained designee, will attempt to contact DiaMedica's assigned Medical Monitor for consultation. No medical help, diagnosis, or advice will be withheld from the subject due to an inability to contact the Medical Monitor. The subject will be encouraged to remain available for follow-up medical monitoring. The Sponsor will be notified as soon as possible of any early withdrawals.

Every effort should be made to complete an Early Withdrawal Visit for a subject that withdraws from the study prior to completing all study requirements. Refer to the **Table 1: Schedule of Assessments** for a description of testing that should occur during the Early Withdrawal Visit. The reasons for early withdrawal will be recorded on the Early Withdrawal eCRF.

## **6 SAFETY OVERSIGHT**

### **6.1 DATA SAFETY MONITORING BOARD (DSMB)**

An independent DSMB will be formed to advise the Sponsor regarding the continuing safety of the trial subjects and those yet to be recruited to the trial, as well as the continuing validity and scientific merit of the trial. At a minimum, the DSMB will meet semi-annually. The committee will be composed of three clinician experts in stroke treatment and a biostatistician who have no affiliation with the clinical study. A DSMB charter will be developed and agreed upon by the Sponsor and DSMB members and will describe the specific functions of the DSMB. The primary responsibilities of the DSMB are to:

- Review and validate the subject sample (i.e., review inclusion/exclusion deviations and other protocol deviations)
- Provide oversight for issues affecting general subject welfare

- Establish study termination guideline criteria
- Recommend premature study termination

At any time during the course of the study, the DSMB may offer opinions or make formal recommendations concerning aspects of the study that impact subject safety (e.g., safety related protocol changes or input regarding adverse event rates associated with the investigational product). Any DSMB recommendations for study modification or termination due to concerns over subject safety or issues relating to data monitoring or quality control will be submitted in writing to the National PI and Sponsor for consideration and final decision.

## 6.2 DEFINITIONS

### 6.2.1 *Adverse Event*

An adverse event (AE) is any untoward medical occurrence in a subject or clinical investigation subject administered a pharmaceutical product and which does not necessarily have to have a causal relationship with the treatment. An AE can therefore be any unfavorable and unintended sign (including an abnormal laboratory finding), symptom, or disease temporally associated with the use of a medicinal (investigational/experimental) product, whether or not related to the product (Refer to International Conference on Harmonization [ICH] E2A: Clinical Safety Data Management: Definitions and Standards for Expedited Reporting, 27 October 1994).

Treatment-emergent AEs will be defined as AEs with an onset after administration of the study treatment, or when a preexisting medical condition increases in severity or frequency after study treatment administration.

Adverse Events (AEs) will not include:

- A medical or surgical procedure such as surgery, endoscopy, tooth extraction, or transfusion (although the condition that leads to the procedure may be an AE)
- A pre-existing disease or condition present at the start of the study that does not worsen during the study
- Any situation where an untoward medical occurrence has not occurred (for example, hospitalizations for cosmetic elective surgery or social admissions)
- An overdose of either the investigational product or a concurrent medication without any resulting signs or symptoms

### 6.2.2 *Serious Adverse Event*

A Serious Adverse Event (SAE) is any AE that:

- Results in death;
- Is life-threatening;
- Requires inpatient hospitalization or prolongation of an existing hospitalization;
- Results in persistent or significant disability/incapacity;

- Is a congenital anomaly/birth defect, or;
- Is a medically important event.
  1. The death of a subject enrolled in a study is per se not an event, but an outcome. Any event resulting in a fatal outcome must be fully documented and reported, regardless of the causality relationship to the investigational product.
  2. The term life threatening refers to an AE in which the subject was at risk of death at the time of the event. It does not refer to an event which hypothetically might have caused death if it was more severe.
  3. Hospitalization is defined as 24 hours in a hospital or an overnight stay. An elective hospital admission to treat a condition present before exposure to the test drug, or a hospital admission for a diagnostic evaluation of an AE, does not qualify the condition or event as an SAE. Further, an overnight stay in the hospital that is only due to transportation, organization, or accommodation problems and without medical background does not need to be considered an SAE.
  4. Medical and scientific judgment should be exercised in deciding whether other situations should be considered serious such as important medical events that may not be immediately life threatening or result in death or hospitalization but might jeopardize the subject or might require medical or surgical intervention to prevent one of the other serious outcomes listed in the above definition. These should also be considered serious. Examples of such events are intensive treatment in an emergency room or at home for allergic bronchospasm, blood dyscrasias, or convulsions that do not result in hospitalization, or development of drug dependency or drug abuse.

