## 2.2 ENDPOINTS

### 2.2.1 Primary Endpoints

The primary endpoint of this study is to evaluate the safety and tolerability of DM199. Endpoints will be assessed as follows:

1. Safety:
  - Incidence, severity and causality of adverse events (AE) and serious adverse events (SAEs)
  - Physical examination changes from baseline (days 4, 22, 56, and 90)
  - Vital sign changes from baseline (resting heart rate, systolic/diastolic blood pressure, respiratory rate, and temperature) (days 1, 4, 7, 10, 13, 16, 19, 22, 56, and 90)
  - Hematology and chemistry parameter changes from baseline (days 4, 22, 56, and 90)
  - 12 lead ECG changes from baseline (days 1, 4, and 22)
2. Tolerability as assessed by incidence and severity of injection site adverse events.

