### ***6.5.1 Completion and Transmission of SAE Reports***

Once an Investigator becomes aware that a SAE has occurred in a study subject, she/he will report the information on the SAE Report Form to the designated Sponsor contract research organization (CRO) within 24 hours. The SAE Report Form will always be completed as thoroughly as possible with all available details of the event and signed by the Investigator or medically qualified designee. If the Investigator does not have all information regarding the SAE, he/she will not wait to receive additional information before reporting the event but rather will update the SAE Report Form when additional information is received.

The Investigator or medically qualified designee will always provide an assessment of causality at the time of the initial report as described in **6.4.3 Assessment of Causality**.

Email transmission of the SAE Report Form is the preferred method to transmit this information to the designated Sponsor CRO. In rare circumstances notification by telephone is acceptable, however, notification via the telephone does not replace the need for the Investigator or medically qualified designee to complete and sign the SAE report form within the outlined time frame.

The Sponsor will provide a list of project contacts for SAE reporting including telephone, email, and fax numbers. Any event that in the opinion of the Investigator may be of immediate or potential concern for the subject's health or well-being will be reported to the Sponsor's Medical Monitor emergency contact.

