#### **8.3.2.1 Adverse Events/Serious Adverse Events**

Adverse events (AEs) will be coded using the Medical Dictionary for Regulatory Activities (MedDRA®) and data will be summarized by System Organ Class (SOC) and Preferred Term (PT). The number and percent of subjects reporting each AE will be summarized for each treatment group and overall. A subject with two or more AEs within the same level of summarization (i.e., SOC or PT) will be counted only once in that level using the most severe (i.e., highest severity/grade) event or most related (for the relationship to study treatment table). Percentages will be based on the number of subjects in the Safety Population within each treatment group. The number of AEs reported will also be presented.

Treatment-emergent AEs (TEAEs) are defined as pre-treatment existing conditions that worsen after study treatment administration, or events that occur during the course of the study during or after administration of study treatment. Only TEAEs will be included in the AE summary tables which will present data by treatment group. In the case of a missing AE start date or stop date, the most conservative approach will be followed.

An overall summary of AEs will be produced including the number of TEAEs; the number and % of subjects reporting at least one: TEAE, serious TEAE, grade 3 or higher TEAE, TEAE related to study treatment (possible, probable), serious TEAE related to study treatment, grade 3 or higher TEAE related to the study treatment, TEAEs by maximum severity and TEAEs by maximum relationship, as appropriate.

Additional AE tables will be generated as follows, as appropriate:

- Overall TEAEs by SOC and PT
- TEAEs by Maximum Severity
- TEAEs by Maximum Relationship to Study Treatment
- Treatment Emergent SAEs

- TEAEs with Grade 3 or Higher
- Study Treatment Related TEAEs by SOC and PT
- Study Treatment Related TEAEs by Maximum Severity

A by-subject AE data listing, including verbatim term, MedDRA SOC and PT, severity, outcome and relationship to study treatment, will be provided. A separate listing will be generated for SAEs.

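### Section 6.2.2, note 3: an AE whose only claim to seriousness is an admission for work-up is not an SAE, so it drops out of the SAE part of the primary endpoint and the 24-hour report

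*Combined protocol and SAP*

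**What the plan says.** Among the seriousness criteria in protocol section 6.2.2 is an AE that "Requires inpatient hospitalization or prolongation of an existing hospitalization". Note 3 explains the term: "Hospitalization is defined as 24 hours in a hospital or an overnight stay". The same note then removes three kinds of stay:

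- elective admission to treat a condition that predates exposure to the drug;
- admission to investigate an AE: "a hospital admission for a diagnostic evaluation of an AE, does not qualify the condition or event as an SAE";
- overnight stays for transport, organisational or accommodation reasons, provided that there is no medical background.

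Note 4 leaves a further route open for medically important events: "Medical and scientific judgment should be exercised in deciding whether other situations should be considered serious".

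SAE status is used in two places that matter here. Sections 2.2.1 and 8.2.1 put the incidence of SAEs in the primary safety endpoint. Section 8.3.2.1 tabulates subjects with at least one serious treatment-emergent AE (TEAE) and adds: "A separate listing will be generated for SAEs". Section 6.5.1 requires an investigator who learns of an SAE to "report the information on the SAE Report Form to the designated Sponsor contract research organization (CRO) within 24 hours".

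**The concern.** The three exclusions in note 3 are not alike. An elective admission for an old condition and a stay for logistic reasons involve no new untoward event, which fits section 6.2.1, where situations without an untoward medical occurrence are not AEs at all. The diagnostic exclusion presupposes an AE and removes it because of the purpose of the admission.

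Many unplanned admissions begin as work-up and become treatment, or are both from the start. Two sites could classify the same overnight stay differently, and the protocol allows up to twelve sites. In a trial whose stated objective is safety and tolerability, that makes a component of the primary endpoint depend on a label. It also removes the 24-hour report for the affected events. Section 6.1 requires the DSMB to meet only semi-annually as a minimum, and section 8.1.4 plans no interim analysis, so prompt SAE reports carry much of the ongoing safety oversight.

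Syncope is a fair example. Sections 1.3 and 9.1 name postural hypotension as a drug-related effect, although it was seen at subcutaneous doses above the 3 µg/kg used here. The documents give no expected frequency for such admissions.

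**Working it through.** The plan attaches no figure to this rule, so there is nothing to reproduce. The check is a reading of the text followed by a bound on its effect.

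**1. Scope of the exclusion.** The sentence in note 3 has two subjects, each with its own article and noun. The qualifiers on elective admission and prior condition sit in the first. The second, quoted above, carries neither, so it covers a new post-dose AE and an unplanned admission.

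**2. A test case.** Take a subject already discharged who has syncope after a dose, is kept in hospital overnight for investigation, and has a negative work-up. Going through the criteria of section 6.2.2:

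- death, life-threatening, disability, congenital anomaly: not met;
- hospitalization: met by the definition (overnight stay), then removed by the diagnostic clause;
- medically important: met only if the investigator so judges under note 4.

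The event is therefore non-serious unless the site calls the stay therapeutic or invokes note 4.

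**3. Consequences.** Under section 8.3.2.1 the event is absent from the serious TEAE count, the SAE table and the SAE listing. Under section 6.5.1 no 24-hour report is due. That section also sends events of concern to the medical monitor, but at the investigator's discretion and without a stated deadline.

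**4. What is not lost.**

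- An event meeting any other seriousness criterion remains an SAE whatever the reason for admission.
- Section 6.3.2 asks for the diagnosis, once available, to be reported as the AE. A confirmed stroke or bleed is judged as such and may well meet another criterion.
- The clause names admission, while the criterion also covers prolongation. AEs that lengthen the index stroke stay are not clearly excluded.
- The event is still recorded as an AE (section 6.3.1). If treatment-emergent it is in the TEAE tables, and if graded 3 or higher it is in those tables too.

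**5. Size per subject.** Section 8.3.2.1 counts subjects, with the arm's Safety Population as denominator. Let x be the number of subjects in an arm whose only serious TEAE would have been such an admission, and n that arm's Safety Population. The SAE rate is understated by x/n.

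- With n = 33 (section 8.1.2, assuming all are dosed) and x = 1: 1/33 = 3.0 percentage points.
- A subject with another serious TEAE contributes nothing to x.

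**6. Illustration under assumed rates.** Let q be the proportion of subjects whose only serious event is an admission for work-up. The documents give no value for q; the range below is an assumption. Expected uncounted subjects per arm = 33q. The chance of at least one in the trial = 1 − (1 − q)^66.

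| q (assumed) | 33q | Chance of at least one in 66 |
|---|---|---|
| 1% | 0.33 | 48% |
| 3% | 0.99 | 87% |
| 5% | 1.65 | 97% |
| 10% | 3.3 | 99.9% |

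The table shows how the effect scales. It does not estimate it.

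**The case against.** The strongest reply is that note 3 narrows only one of six criteria and that the rest, including the broad medically-important route in note 4, catch what matters. On this view the loss is mainly benign or negative work-ups. These stay visible as AEs, and AE incidence and severity belong to the same primary endpoint. The dosing rules in section 4.5 use grade and relatedness, not SAE status. The study is descriptive (section 8.3), so no test is distorted.

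Most of this stands, and it sets the limits of the point. It does not remove the point. Note 4 replaces an observable criterion (24 hours or overnight) with individual judgment, and visibility in the AE tables supplies neither the SAE count nor the 24-hour report.

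Two stronger readings are tempting and are not supported:

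- A reader might infer that suspected strokes, suspected bleeds or early neurological worsening would in general go uncounted. Confirmed diagnoses may well requalify. Worsening during the index stay is a question of prolongation, which the clause does not name.
- A reader might see a contradiction with Table 4, where an AE with hospitalization indicated is Grade 3 and no diagnostic exception appears. Section 6.4.1 expressly separates severity from seriousness, so a Grade 3 non-serious event is consistent with the protocol.

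**Conclusion.** The point holds in a limited form. For an AE whose sole seriousness criterion is an admission for work-up, note 3 removes SAE status, the place in the SAE part of the primary endpoint, and the 24-hour report. Its direction is fixed: following the rule can only lower the SAE count. Its application will vary with how sites label a stay.

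The size of the undercount cannot be derived from the documents. The per-subject step of about 3 points assumes that all 33 subjects in an arm are in the Safety Population and that the subject has no other serious TEAE. A reader might go on to assume one to three such subjects on DM199 and conclude that its SAE rate is understated by 3 to 9 points (1/33 to 3/33). Nothing in the documents supports those counts or their restriction to one arm. The rule applies to both arms of a double-blind trial, so what is shown is under-ascertainment, not bias between arms.

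The change is worth making because it is cheap and bears on a primary safety component. The point does not call the trial's design into question.

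**What to change.** In note 3 of section 6.2.2, delete the words that exclude a hospital admission for diagnostic evaluation of an AE. Keep the exclusion for elective admission for a condition present before exposure, and the exclusion for logistic stays without medical background. The hospitalization criterion then applies to new AEs by length of stay, without a diagnostic or therapeutic label. No change to section 6.5.1 or 8.3.2.1 is needed, since both follow the definition.

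Cost: one clause deleted, a few more SAE reports for sites and the CRO to process, and a slightly less favourable SAE count.

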### **6.2.3 Adverse Drug Reaction (ADR)**

In the pre-approval clinical experience with a new medicinal product or its new usage, particularly as the therapeutic doses may not be established, all noxious and unintended responses to a medicinal product related to any dose should be considered adverse drug reactions. The phrase “responses to a medicinal product” means that a causal relationship between a medicinal product and an AE is at least a reasonable possibility, i.e. the relationship cannot be ruled out.

